**Pilot Study of Normative Range of Field of Binocular Single Vision in Adults in Singapore
(NORVIBAS)**

Study Site: Tan Tock Seng Hospital, Singapore

Principal Investigator:

[name] [name]

Associate Consultant

NHG Eye Institute,

Tan Tock Seng Hospital

NHG Health, Singapore

Co-Investigators(s):

[name] [name]

Senior Orthoptist

NHG Eye Institute,

Tan Tock Seng Hospital

NHG Health, Singapore

[name] [name]

Senior Orthoptist

NHG Eye Institute,

Tan Tock Seng Hospital

NHG Health, Singapore

[name] [name]

Orthoptist

NHG Eye Institute,

Tan Tock Seng Hospital

NHG Health, Singapore

[name] [name]

Consultant

NHG Eye Institute,

Tan Tock Seng Hospital

NHG Health, Singapore

[name] [name]

Clinical Research Coordinator

NHG Eye Institute,

Tan Tock Seng Hospital

NHG Health, Singapore

Background:

The assessment and monitoring of the field of binocular single vision is a crucial aspect of ophthalmological care, particularly in the management of oculoplastic and strabismus. Currently, clinicians worldwide, including those in Singapore, rely on the normal boundary of the field of binocular single vision established by Doctor Robert M. Feibel & Gill Roper-Hall in 1974 as the gold-standard parameter for clinical assessment. However, this long-standing standard raises several significant concerns regarding its applicability to our current population.

The original study by Feibel & Roper-Hall was conducted in St Louis, Missouri, United States of America, with participants who were likely of Caucasian descent. This demographic composition presents a potential limitation when applying these standards to Asian populations, particularly in Singapore, where ethnic and genetic factors may influence ocular characteristics.

Furthermore, the study's methodology involved only "several" normal individuals, suggesting a sample size of more than two but fewer than ten participants. A sample size of this limited scope significantly increases the likelihood of Type II errors, potentially compromising the statistical power and reliability of the established normative values.

The temporal gap of over five decades since the original study adds another layer of concern.

Population characteristics, environmental factors, and lifestyle patterns have undergone substantial changes during this period, potentially affecting ocular health parameters.

Additionally, advances in measurement techniques and an understanding of ocular physiology suggest the need for updated normative data that reflect current population characteristics and incorporate modern assessment methodologies.

Given these limitations, there is a pressing need to establish population-specific normative data for the field of binocular single vision in Singapore's adult population. This would not only provide more relevant reference values for clinical assessment but also potentially improve the accuracy of diagnosis and monitoring of various ocular conditions in our local context.

Study Objectives

The primary purpose of this pilot study is to address these gaps in current clinical practice through two main objectives. First, we aim to establish the normative range of the field of binocular single vision specifically for adults in Singapore, creating a locally relevant reference

standard. This will provide clinicians with more appropriate benchmarks for assessing their patients.

Secondly, we seek to determine whether a significant difference exists between these local normative values and the currently used standards established by Feibel & Roper-Hall in 1974. We hypothesise that there will be a significant difference in the normative range of the field of binocular single vision in our current adult population in Singapore compared to the historical standards. This hypothesis is based on the understanding that genetic, environmental, and temporal factors may influence ocular characteristics.

The findings from this study could have substantial clinical implications. If significant differences are identified, it would justify the adoption of new, population-specific normative values for clinical practice in Singapore. This could lead to more accurate assessment and monitoring of subjects, potentially improving the quality of eye care delivered to our population. Furthermore, this study could serve as a model for other Asian countries to establish their population-specific normative values, contributing to the broader field of ophthalmology in the region.

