2. STUDY DESIGN

This research will be conducted as a single-centre, pilot study at Tan Tock Seng Hospital, designed as an observational investigation regulated under the Human Biomedical Research Act (HBRA) of Singapore. This study will employ a cross-sectional design, with each participant completing all assessments in a single visit lasting approximately 60 minutes. This approach has been chosen to minimise participant burden while ensuring comprehensive data collection.

The study will span a total duration of one year, with active data collection scheduled from 1 November 2025 to 31 October 2026. This timeline allows for adequate recruitment, data collection, and subsequent analysis while accounting for potential scheduling challenges and the need for careful quality control of the collected data. The single-visit design also helps minimise dropout rates and ensures consistency in data collection procedures.

Study Design:

Study population: This study aims to recruit a balanced sample of adult participants from Singapore's population, with a target enrolment of 32 participants, equally distributed between males and females (16 of each gender) and of Asian descent. This sample size has been

carefully determined to provide sufficient statistical power while remaining feasible within the study's resources and timeline.

Participants will be recruited primarily by word of mouth at the TTSH Ophthalmology Specialist Outpatient Clinic's, focusing on accompanying next-of-kin of existing patients, TTSH staff members, or any other available healthy volunteers after meeting the inclusion and exclusion criteria. The recruitment process will be conducted with careful attention to avoiding any coercion or undue influence, particularly in cases involving dependent relationships. All potential participants will be given adequate time to consider their participation and will be required to provide informed consent in the presence of a witness in compliance to the Declaration of Helsinki, as well as other prevailing laws and guidelines regulating clinical research.

Inclusion Criteria:

1. Age: 21 to 59 years old
2. Gender: Males or females
3. Ethnicity: Asian descent.
4. Language comprehension: Able to understand verbal spoken instructions in:
 - British/American English
 - Mandarin Chinese
 - Bahasa Melayu
5. Protocol compliance: Ability to comply with the study protocol, as determined by the investigator's judgment

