6. Consent capacity: Must be able to understand and provide informed consent, with signed informed consent form required before any study assessments

Exclusion Criteria:

1. Communication barrier: Unable to understand verbal spoken instructions
2. Medical history:
 - Any facial trauma
 - Any ocular trauma
 - Any head trauma
 - Any history of ocular disease
 - Any history of ocular surgery
 - Systemic condition(s)

3. Near visual acuity:

- Right eye & Left eye monocularly, binocularly unaided near vision: worse than N6 at 40cm from participant's nose

4. Ocular alignment:

- Prism cover test at near (30cm) of equal or greater than 10 prism diopters at these positions of gaze:

- Primary gaze
- Right gaze
- Left gaze
- Up gaze
- Down gaze

5. Extraocular movement:

- Extraocular movement of over-action or under-action of equal or greater than 0.5 in any of the nine cardinal positions of gaze

6. Confrontational Visual field:

- Abnormal monocular visual field on confrontational visual field test

7. Hess chart test

- Abnormal or asymmetry in pattern of extraocular muscle action in Hess chart test

8. Pregnant woman will be excluded from this study.

Study Procedure:

This cross-sectional study will involve 1 study visit.

Pre-specified clinical outcome: The primary outcome is the establishment of a normative range of field of binocular single vision measurements in Singapore adults. These measurements will be taken using the Takagi MT-325UD Projection Perimeter. The secondary outcome is the comparison with the normal boundary of the established field of binocular single vision by Feibel & Roper-Hall (1974) and the analysis of any significant differences between the two sets of measurements.

Clinical Validation will be a cross-sectional study design to determine the normative range of the field of binocular single vision measurements in participants who are Singapore adults focusing on accompanying next-of-kin of existing participants and TTSH staff members after meeting the inclusion and exclusion criteria.

Research Procedures:

1) *Medical history assessment*

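### Significance against the 1974 boundary is given as the ground for adopting new norms, but no relevant difference is stated

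*Protocol*

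**What the plan says.** The second aim in the protocol's Study Objectives is to "determine whether a significant difference exists between these local normative values and the currently used standards". The hypothesis that follows is that such a difference exists; it gives no size and no margin. The same section then states the consequence: "If significant differences are identified, it would justify the adoption of new, population-specific normative values for clinical practice in Singapore".

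Under Pre-specified clinical outcome, the protocol says: "The secondary outcome is the comparison with the normal boundary of the established field of binocular single vision". The same sentence adds an analysis of whatever significant differences appear between the two sets of measurements.

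The Study population paragraph describes the sample size as "carefully determined to provide sufficient statistical power". The Sample size calculation section, however, contains no difference to be detected. It takes an SD of 6 from a literature range of 5.3 to 6.9, sets a precision of 2.2 for the mean at 95% confidence, arrives at 29, and allows for dropout to reach 32. It does not name the measure or its unit, and it does not call 2.2 a clinically relevant difference.

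**The concern.** The 1974 boundary is the reference that clinicians now use. Whether it should be replaced depends on how well it fits healthy local adults: how far their fields lie from it, and how many fall inside it. A significance criterion answers a different question, namely whether chance alone could plausibly explain the observed difference. The answer depends on sample size and SD as well as on the size of the difference.

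Without a stated relevant difference, a small shift could be reported as grounds for new norms. The problem is sharper if the boundary is a limit rather than an average, because a limit that fits well is meant to lie away from the mean. The protocol does not say which it is taken to be. At stake is what the secondary result may be taken to conclude.

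**Working it through.** **Inputs.** From the Sample size calculation section: SD 6 (range 5.3 to 6.9), precision 2.2, 95% confidence, 29 evaluable, dropout up to 10%, 32 enrolled. Assumed here, because the protocol does not state them: a two-sided 5% one-sample t test of the mean, the 1974 boundary treated as a fixed line on the same scale as the measure, and a normal distribution.

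**1. The plan's own figure.** n = (1.96 × SD / d)² = (1.96 × 6 / 2.2)² = 28.57, rounded up to 29. For dropout, 29 × 1.10 = 31.9 gives 32, while 29 / 0.90 = 32.2 would give 33; the stated 32 is close enough. The figure reproduces, and it concerns the precision of a mean only.

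**2. Smallest observed shift that would be significant.** t(0.975, 28) = 2.048, and 2.048 / √29 = 0.380 SD.

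| SD | 0.380 × SD |
|---|---|
| 5.3 | 2.02 |
| 6 | 2.28 |
| 6.9 | 2.62 |

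**3. What a shift of that size means.** It depends on what the boundary is.
- If the boundary is an average, 50% of healthy adults fall inside it when it fits. After a shift of 0.380 SD the share is Φ(±0.380), that is 35% or 65%.
- If the boundary is a lower limit at the 2.5th percentile, the share moves from 2.5% to Φ(−1.96 ± 0.380), that is 1.0% or 5.7%.

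The same just-significant result therefore corresponds to quite different changes in fit.

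**4. A limit that fits exactly.** Suppose the boundary lies at the local 2.5th percentile. The mean is then 1.96 × SD away: 10.4, 11.8 or 13.5 units for SD 5.3, 6 or 6.9. The expected t is about 1.96 × √29 = 10.6, against a critical value of 2.048. For a limit at the 5th percentile it is 1.645 × √29 = 8.9, and at the 10th percentile 1.282 × √29 = 6.9. Significance is practically certain in each case, although the limit is doing what it was set to do.

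**5. Significance and share inside the line, side by side** (SD 6, n = 29; share = Φ(−distance / SD), probability from the noncentral t distribution).

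| Line below the healthy mean by | Healthy adults falling inside it | Probability of significance |
|---|---|---|
| 0 | 50% | 5% |
| 2.28 | 35% | 51% |
| 5 | 20% | 99% |
| 9.87 | 5% | about 100% |

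Under a limit reading, the fewer healthy adults the line cuts off, the more surely the test is significant.

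**6. Precision of the alternative.** The exact (Clopper-Pearson) 95% interval for 0 of 29 is 0 to 1 − 0.025^(1/29) = 11.9%. For 3 of 29 it is 2.2% to 27.4%.

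**The case against.** **No test is specified.** The protocol names no one-sample t test, no alpha and no comparison of a mean with a fixed line. The hypothesis speaks of the normative range, and the mean appears only in the sample size section. Test and alpha may properly sit in an analysis plan that is not shown. This stands, and it makes every figure in steps 2 to 5 illustrative. It does not remove the point: a test and an alpha would not repair a sentence that makes significance the ground for adoption.

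**Significant may mean clinically important.** The Background uses the word loosely, and the adoption sentence follows one about clinical implications. That reading is possible, although the reference to statistical power leans the other way. On the clinical reading a threshold is still needed, and none is given.

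**Average or limit is a property of the cited 1974 study.** This stands. Step 4 holds only if the boundary is a limit on the same scale as the unnamed measure. Nor does the protocol say that anyone falling inside the line would be labelled abnormal.

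**Stronger readings that the protocol does not support.**
- A reader might infer that a non-significant result would be taken as a reason to keep the 1974 line. The protocol never says so.
- A reader might also infer that a difference will be attributed to population or era, which the design could not support: "This study will employ a cross-sectional design, with each participant completing all assessments in a single visit", with no concurrent comparison group. But "This hypothesis is based on the understanding that genetic, environmental, and temporal factors may influence ocular characteristics" only motivates the hypothesis, and no objective or outcome assigns a cause. The Background openly gives other reasons for new norms, describing the 1974 group as "suggesting a sample size of more than two but fewer than ten participants" and saying that "advances in measurement techniques and an understanding of ocular physiology suggest the need for updated normative data".

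**The percentage is imprecise at this size.** True: an upper limit of 11.9% with no one inside the line cannot separate 2.5% from 5.7%. That limits what the pilot can settle, and is itself a reason for a more modest adoption sentence.

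**Conclusion.** The point holds in a narrow form and is minor. The protocol offers significant differences as justification for adopting new norms and repeats the criterion in the secondary outcome. It states no relevant difference, and it sizes the study only for the precision of a mean. Significance by itself would not show how well the 1974 boundary fits healthy local adults.

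On the assumptions listed, an observed shift of about 2.3 units (2.0 to 2.6) would be enough for significance. A limit placed exactly at the local 2.5th percentile would almost certainly test as different from the mean; that second result is conditional on the boundary being a limit on the measure's scale. It should not be read as a prediction that a sound boundary will be rejected in this study.

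The sentence is rationale in a self-described pilot, and the primary outcome, the local range, does not depend on the comparison.

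**What to change.** 1. Restate the secondary objective as estimating how well the 1974 boundary fits healthy local adults.
2. Before analysis, state whether the boundary is treated as an average or a limit, and which difference or percentage the investigators regard as relevant, in the unit of the selected measure.
3. Report, per direction of gaze or for the selected measure, the difference from the boundary with a 95% confidence interval and the percentage of healthy participants falling inside it with an exact 95% interval. Falling inside means that the participant's limit of single vision lies within the boundary in that direction, or that the score is below the boundary's score if one summary measure is used. If the boundary is treated as a limit, judge fit by the percentage rather than the mean.
4. Replace the adoption sentence with: *The size of any difference and the percentage of healthy participants falling inside the 1974 boundary will inform whether local reference values should be developed further.*

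Cost: rewording one objective and one sentence, one decision taken in advance, and two estimates from data already being collected. No extra participants or visits are needed. The price is a weaker claim and a wide interval for the percentage, so the pilot can inform adoption but not settle it.

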2. STUDY DESIGN

This research will be conducted as a single-centre, pilot study at Tan Tock Seng Hospital, designed as an observational investigation regulated under the Human Biomedical Research Act (HBRA) of Singapore. This study will employ a cross-sectional design, with each participant completing all assessments in a single visit lasting approximately 60 minutes. This approach has been chosen to minimise participant burden while ensuring comprehensive data collection.

The study will span a total duration of one year, with active data collection scheduled from 1 November 2025 to 31 October 2026. This timeline allows for adequate recruitment, data collection, and subsequent analysis while accounting for potential scheduling challenges and the need for careful quality control of the collected data. The single-visit design also helps minimise dropout rates and ensures consistency in data collection procedures.

Study Design:

Study population: This study aims to recruit a balanced sample of adult participants from Singapore's population, with a target enrolment of 32 participants, equally distributed between males and females (16 of each gender) and of Asian descent. This sample size has been

carefully determined to provide sufficient statistical power while remaining feasible within the study's resources and timeline.

Participants will be recruited primarily by word of mouth at the TTSH Ophthalmology Specialist Outpatient Clinic's, focusing on accompanying next-of-kin of existing patients, TTSH staff members, or any other available healthy volunteers after meeting the inclusion and exclusion criteria. The recruitment process will be conducted with careful attention to avoiding any coercion or undue influence, particularly in cases involving dependent relationships. All potential participants will be given adequate time to consider their participation and will be required to provide informed consent in the presence of a witness in compliance to the Declaration of Helsinki, as well as other prevailing laws and guidelines regulating clinical research.

Inclusion Criteria:

1. Age: 21 to 59 years old
2. Gender: Males or females
3. Ethnicity: Asian descent.
4. Language comprehension: Able to understand verbal spoken instructions in:
 - British/American English
 - Mandarin Chinese
 - Bahasa Melayu
5. Protocol compliance: Ability to comply with the study protocol, as determined by the investigator's judgment
6. Consent capacity: Must be able to understand and provide informed consent, with signed informed consent form required before any study assessments

Exclusion Criteria:

1. Communication barrier: Unable to understand verbal spoken instructions
2. Medical history:
 - Any facial trauma
 - Any ocular trauma
 - Any head trauma
 - Any history of ocular disease
 - Any history of ocular surgery
 - Systemic condition(s)

3. Near visual acuity:

- Right eye & Left eye monocularly, binocularly unaided near vision: worse than N6 at 40cm from participant's nose

4. Ocular alignment:

- Prism cover test at near (30cm) of equal or greater than 10 prism diopters at these positions of gaze:

- Primary gaze
- Right gaze
- Left gaze
- Up gaze
- Down gaze

5. Extraocular movement:

- Extraocular movement of over-action or under-action of equal or greater than 0.5 in any of the nine cardinal positions of gaze

6. Confrontational Visual field:

- Abnormal monocular visual field on confrontational visual field test

7. Hess chart test

- Abnormal or asymmetry in pattern of extraocular muscle action in Hess chart test

8. Pregnant woman will be excluded from this study.

Study Procedure:

This cross-sectional study will involve 1 study visit.

Pre-specified clinical outcome: The primary outcome is the establishment of a normative range of field of binocular single vision measurements in Singapore adults. These measurements will be taken using the Takagi MT-325UD Projection Perimeter. The secondary outcome is the comparison with the normal boundary of the established field of binocular single vision by Feibel & Roper-Hall (1974) and the analysis of any significant differences between the two sets of measurements.

Clinical Validation will be a cross-sectional study design to determine the normative range of the field of binocular single vision measurements in participants who are Singapore adults focusing on accompanying next-of-kin of existing participants and TTSH staff members after meeting the inclusion and exclusion criteria.

Research Procedures:

1) *Medical history assessment*

A comprehensive medical history will be obtained from each participant through a structured interview. The investigator will specifically inquire about any history of facial trauma, ocular trauma, head trauma, ocular disease, ocular surgery or any systemic condition(s), documenting the nature, timing, and severity of any reported incidents. Particular attention will be paid to any previous ocular diseases and surgical interventions. All responses will be recorded in standardized case report forms, with detailed documentation of the type, date, and outcome of any reported conditions or procedures. Participants should not have any history of facial trauma, ocular trauma, head trauma, ocular disease, ocular surgery or any systemic condition(s). This thorough screening is essential to ensure participants meet the study criteria for establishing normative values.

2) *Near Visual Acuity Testing*

Near visual acuity will be assessed right eye and left eye monocularly & binocularly using a standard near vision chart held at 40cm from the participant's nose. Testing will be conducted under standardized lighting conditions with monocularly and binocularly and unaided. A measuring stick will be used to maintain the precise testing distance. The examiner will record the smallest line that can be read accurately, with participants required to achieve N6 or better to be included in the study. Any participant with near vision worse than N6 will be excluded from the study.

3) *Ocular Alignment Assessment*

A prism cover test will be performed at near of approximately 30cm from participant's nose to evaluate ocular alignment. The examiner will systematically assess alignment in five positions of gaze: primary gaze (straight ahead), right gaze, left gaze, up gaze, and down gaze. Measurements will be taken using loose prisms or a prism bar, with deviations recorded in prism diopters. Any deviation equal to or greater than 10 prism diopters in any of the five positions of gaze will result in exclusion from the study. The examiner will ensure consistent testing distance using a measuring stick and maintain standardized testing conditions throughout the assessment.

4) Extraocular Movement Testing

Extraocular muscle function will be examined by having the participant follow a fixation target through the nine cardinal positions of gaze. The examiner will assess and grade any overaction or underaction of the extraocular muscles using a standardized scale, where 0 represents normal movement. Participants demonstrating overaction or underaction equal to or greater than 0.5 units in any direction will be excluded from the study. The examination will be conducted methodically, ensuring smooth pursuit movements are carefully observed and documented.

5) Confrontational Visual Field Testing

Monocular confrontational visual field testing will be performed separately for each eye. The examiner will sit at one meter distance, directly facing the participant at eye level. Each quadrant of the visual field will be tested systematically using standardized targets, while the participant maintains fixation on the examiner's nose. Any abnormality in the visual field will be documented and will result in exclusion from the study. The testing sequence will remain consistent for all participants to ensure standardization of the assessment.

6) Hess Chart Testing

The Hess chart test will be conducted using a standard Hess screen at the recommended testing distance. This test will evaluate the action of each extraocular muscle, with results plotted on the Hess chart. The examiner will assess for any asymmetry or abnormality in the pattern of extraocular muscle action. Any abnormal findings on the Hess chart will be documented in detail and will result in exclusion from the study. The test will be performed following standardized protocols to ensure consistency and accuracy of results.

7) Field of binocular single vision

Participants perform the field of binocular single vision test binocularly and pursue a single round light stimulus presented in the bowl of the Takagi MT-325UD Projection Perimeter, and participants will need to look and follow through the single light stimulus as it moves throughout the bowl, and participants will press the buzzer if two distinct light stimuli are seen. Scores will be recorded and plotted on the recording sheet based on participants' responses during the test. Eye dilation will not be required for this research study.

All examinations will be performed by trained orthoptists, with results recorded immediately in standardised documentation forms. The testing sequence will remain consistent across all participants, and any exclusion criteria met will be documented with specific measurements and observations.

As part of the clinical evaluation of participants during the analysis phase, access and extraction of data will be limited to TTS's NGEMR and Zeiss Forum Viewer. Clinical information collected for this study would include medical & ocular histories along with prior visual assessments documented by orthoptists.

Additionally, NEHR cannot and will not be used for research. Access of medical records for the purpose of data collection will also be limited to the period dated from 1 November 2025 to 31 October 2026. Clinical information/data collected will be done once off during, or retrospectively after the study visit.

Sample size calculation

This is a pilot study. Due to resource constraints, a total of 32 healthy participants will be recruited for this study.

Based on the literature, the standard deviation (SD) of normal values for the selected binocular single vision measure ranges from 5.3 to 6.9. Assuming an SD of 6 in our study, a sample size of 29 will allow us to estimate the mean of normal values with a precision of 2.2 at the 95% confidence level. We expect drop out rate to be no more than 10%, 32 participants will be sufficient.

References:

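### The protocol says 32 participants were chosen for sufficient statistical power, but its only calculation is a precision target for a mean

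*Protocol*

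**What the plan says.** The protocol accounts for the enrolment figure in two places.

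- **Section 2, Study Design, Study population.** The target of 32 (16 men, 16 women) is described as "carefully determined to provide sufficient statistical power while remaining feasible". The sentence goes on to name the study's resources and timeline as the limits on feasibility.
- **Sample size calculation.** After labelling the study a pilot, it states: "Due to resource constraints, a total of 32 healthy participants will be recruited for this study". It then takes an SD of 6 from a literature range of 5.3 to 6.9 and says that "a sample size of 29 will allow us to estimate the mean of normal values with a precision of 2.2", at 95% confidence. It closes with: "We expect drop out rate to be no more than 10%, 32 participants will be sufficient".

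Two other parts of the protocol bear on what power would mean here.

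- **Background** criticises the 1974 reference study for a sample so small that it "significantly increases the likelihood of Type II errors, potentially compromising the statistical power and reliability of the established normative values".
- **Study Objectives** gives the hypothesis as the second aim: "We hypothesise that there will be a significant difference in the normative range of the field of binocular single vision", relative to the 1974 standard. The Study Procedure section makes that comparison the secondary outcome.

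**The concern.** Power is a property of a test against a stated difference. The Study population paragraph claims enough of it, but the section that derives the number calculates something else, the width of a confidence interval for one mean. The protocol therefore credits its design with a property that it does not demonstrate.

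The word matters because the protocol has a hypothesis to which power would apply, the difference from the 1974 standard. The Background also links power to Type II error, so a reader may fairly take the later claim in the technical sense. If the comparison then turns out non-significant, the statement that power was sufficient could be cited to argue that local values agree with the 1974 standard. A precision target for a local mean gives no basis for that conclusion.

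**Working it through.** **Inputs, all from Sample size calculation:** SD 6 (literature range 5.3 to 6.9); 29 evaluable; precision 2.2, read as the half-width of a two-sided 95% interval; dropout at most 10%; 32 recruited.

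**Step 1: reproduce the protocol's figure.**

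- n = (1.96 × SD / half-width)² = (1.96 × 6 / 2.2)² = 28.57, rounded up to 29.
- Half-width at n = 29: 1.96 × 6 / √29 = 2.18. Over the SD range it is 1.93 (SD 5.3) to 2.51 (SD 6.9).
- Dropout: 10% of 32 is 3.2, so at most 3 people are lost, and 32 − 3 = 29 remain.

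The calculation is sound for what it sets out to do.

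**Step 2: look for the ingredients of a power statement.**

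| Ingredient | In the protocol? |
|---|---|
| SD | Yes, 6 |
| Number evaluable | Yes, 29 |
| Confidence level for an interval | Yes, 95% |
| Difference to be detected | No |
| Significance level for a test | No |
| Power | No |

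The missing items are those that separate power from precision. No power figure can be derived from the protocol.

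**Step 3: one illustration that precision does not stand in for power.** This rests on assumptions that are not in the protocol: a two-sided 5% one-sample t-test, the 1974 value treated as a fixed constant, and a true difference equal to the stated precision of 2.2.

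- Noncentrality = (2.2 / 6) × √29 = 1.97, on 28 degrees of freedom.
- Power is about 48% at SD 6 (58% at SD 5.3, 38% at SD 6.9).

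A value near one half is expected whatever the study. A difference equal to the interval's half-width lies almost exactly on the boundary of significance. The figure shows only that meeting the precision target does not deliver power for a difference of the same size.

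**The case against.** **Loose wording.** The strongest reply is that this is one loosely worded summary sentence. The section headed Sample size calculation is the operative text, and both places give 32. The Study population sentence itself mentions resources, so the two accounts agree on that limit. The Background attaches power to the reliability of normative values and describes no hypothesis test in the 1974 work, so the authors may simply mean a sample large enough for a usable estimate. Much of this stands. The disagreement is confined to the word power, and that is why the point is minor. It does not remove the point: the same Background sentence names Type II errors, the protocol states a hypothesis of a significant difference, and even on the loose reading the word does not describe what was calculated.

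**Conjectural harm.** No passage says a non-significant result will be taken as agreement. That is true. The proposed wording closes off such a reading and does not correct a stated plan.

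**Stronger readings to avoid.** A reader might infer that the study is underpowered. The documents do not support this, because no target difference is given against which power could fall short; the 48% above rests on assumed inputs. A reader might also infer that 32 is the wrong number, but the precision calculation reproduces. Nor does the adoption sentence in Study Objectives, "If significant differences are identified, it would justify the adoption of new, population-specific normative values for clinical practice in Singapore", need rewriting on this account. It concerns significant results, whereas an unsupported power claim bears mainly on non-significant ones. Finally, the absence of a named test is no part of the point, since a statistical analysis plan that is not shown may supply it.

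**Conclusion.** The point holds, as a minor one. The claim of sufficient power is unsupported by the only sample size calculation in the protocol, which is a precision target for a mean set within resource limits. The gap matters most for the secondary comparison with the 1974 standard, which that calculation does not address.

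This conclusion comes from comparing the two sections and needs no assumption. Only the 48% illustration does, and the conclusion does not depend on it. Whether the precision of a mean is the right target for a normative range is a separate question, not judged here.

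**What to change.** In section 2, Study Design, Study population, replace the sentence on how the sample size was determined with, for example:

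*The sample size was set by available resources and a precision target for the mean (see Sample size calculation); it was not based on power for the comparison with the 1974 standard, so that comparison will be reported as an estimate with a 95% confidence interval and a non-significant result will not be read as agreement with the 1974 standard.*

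If a statistical analysis plan exists, its wording on the comparison should agree. Power and detectable-difference figures should stay out of the protocol, because they would rest on inputs that it does not contain. Study Objectives and Sample size calculation need no change for this point.

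The cost is one sentence, with no added participants, visits or data. The drawback is that the sample size is described less favourably than now.
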